4.1 Example of the BLRM using BMS-986207 Monotherapy Dose Escalation

[figure not shown]
According to safety consideration and clinical judgement, the dose level 80 mg is recommended as the starting dose for BMS-986207 monotherapy. With the current BMS-986207 prior specified in the [Section 1.2.1](#) and all available DLT information up to 240 mg, a corresponding decision tree illustrating various models' recommendations under all possible scenarios (for dose levels of 800 mg and 1600 mg) is provided in [Figure 4](#).

Tracing a branch of the decision tree in [Figure 4](#) illustrates the decision making process. Taking the left-most branch of the tree as an example, starting at 80 mg, there was 0 DLT observed at 80 mg in the real clinical trial, the model recommended to escalate to 240 mg (The BLRM actually recommends escalating to dose level 800 mg but since this is a 10 fold increase of dose and this

type of dose skipping is not allowed the dose level 240 mg is selected), one level above the current treated dose level according escalation rules per protocol (as detailed in Protocol [Section 5.1](#)). Additionally, there was 0 DLT observed at 240 mg in real data, the model recommended to escalate further one dose level to 800 mg.

As illustrated in Figure 4, there are 6 potential decision paths for dose levels 800 mg and moving onwards up to 800 mg. During the actual clinical study, the tree would be narrowed or deepened based on actual DLT. The clinical team will be able to leverage this decision tree to preview decisions at each interim monitoring step and to plan proactively.

Figure 4: **The BLRM model hypothetical decision tree for BMS-986207 monotherapy during dose escalation (up to 800 mg; E: escalation; S: stay; DE: de-escalation)**

5 BOIN ESCALATION DESIGN SIMULATION WITH 2 DOSE LEVELS, PART 1C

The Bayesian optimal interval (BOIN) design framework will be used to guide the safety evaluation of BMS-986207 in combination with nivolumab and ipilimumab in Part 1C. The design is typically also used to determine maximum tolerated dose (MTD) selection in cases where more doses are evaluated.^{5,6}

As a single dose level of BMS-986207 will be evaluated in this triplet combination (with potential for a de-escalation if needed), the goal in this study part is to assess if the dose is tolerable. Therefore MTD reference below (as in typical multi-dose level design) represents a ‘tolerable

dose' in Part 1C. As an escalation decision is not of interest in Part 1C, a design recommendation to declare a dose as tolerable is based on meeting the same criteria needed to escalate.

The target toxicity rate for the MTD is $\phi = 0.3$ and the maximum sample size is 12. Participants will be enrolled in cohorts of 3. The BOIN design framework uses the following rule optimized to minimize the probability of incorrect dose assignment, to guide dose escalation/de-escalation:

- If the observed DLT rate at the current dose is ≤ 0.236 , declare the dose tolerable;
- If it is ≥ 0.359 , de-escalate the dose to the next lower dose level;
- Otherwise, stay at the current dose.

The design MTD selection approach described next, is included for general information on the design; however, it is not used in this study. After the trial is completed, selection of the MTD is based on isotonic regression as specified in Liu and Yuan (2015).⁵ Specifically, the MTD is the dose for which the isotonic estimate of the DLT rate is closest to the target DLT rate. If there are ties, select the higher dose level when the isotonic estimate is lower than the target DLT rate and select the lower dose level when the isotonic estimate is greater than or equal to the target DLT rate.

5.1 Operating characteristics of BOIN design with 2 dose levels

Table 6 shows the operating characteristics of the trial design based on 1000 simulations of the trial using the BOIN Design Desktop Program.⁷ The operating characteristics show that the design selects the true MTD (tolerable dose), if any, with high probability and allocates more patients to the dose levels with the DLT rate closest to the target of 0.3.

Table 6: Operating Characteristics of the BOIN Design

	Dose Level		Number of Participants	% Early Stopping
	1	2		
Scenario 1				
True DLT Rate	0.30	0.48		
Selection %	60.8	31.9		7.3
% Pts Treated	40.8	59.2	11.8	
Scenario 2				
True DLT Rate	0.16	0.30		
Selection %	22.1	77.8		0.1
% Pts Treated	16.3	83.7	12.0	

Scenario 3

True DLT Rate	0.20	0.35	
Selection %	33.7	65.2	1.1
% Pts Treated	22.9	77.1	12.0

Abbreviations: BOIN, Bayesian optimal interval; DLT, dose limiting toxicity. Pts, participants.

Note: "% Early Stopping" refers to early stopping due to excessive DLTs.

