5.1.2.6 Safety Evaluation Phase of Part 1C

Up to 18 participants per dose level tested will be treated in the Triplet Cohort. BMS-986207 will be administered at 600 mg and/or 360 mg q3w and nivolumab will be administered at 360 mg q3w. Ipilimumab, at a dose of 1 mg/kg, will be given q6w. The DLT period in Part 1C will be 42 days (6 weeks).

A dose of 1200 mg BMS-986207 administered every 3 weeks has been tested per Amendment 03 but due to the DLTs observed no additional participants will be tested at this dose (see [Section 3.2.1.4](#)).

The DLT safety monitoring during the dose evaluation phase, including the potential decision to de-escalate to a lower dose, will be based on the BOPIN design framework with target toxicity (DLT) rate of 30% (24%, 36%), as presented in [Table 5.1.2.6-1](#).^{23,24} The BOPIN design takes a very simple form, rendering it easy to implement in practice. It is more straightforward and transparent than other model-based and model-assisted methods. The decisions on dose tolerability guided by the design are based on comparing the observed DLT rate at the current dose with a pair of fixed dose escalation and de-escalation boundaries. This allows generation of a decision table that guides DLT assessment depending on the number of participants treated and observed DLTs. The performance of the design based on the operating characteristics is shown in [Appendix 12](#).

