As a dose escalation is not planned in Part 1C, a design recommendation to declare a dose as tolerable is based on meeting the same criteria needed to escalate. A minimum of 6 DLT evaluable participants will be required in Part 1C to declare a dose tolerable for initiation of Part 2C. In addition, to better estimate tolerability of the dose level in combination with nivolumab and ipilimumab, more participants will be treated even if a dose is declared tolerable with n=6, for up to a total of 18 treated. In contrast, a design recommendation “Stay” indicates that this dose level needs to be evaluated further for safety to declare this dose tolerable. In that case, additional cohorts of 3-4 or more participants (depending on the number of observed DLTs) will be treated up to a total of 18. If dose-de-escalation is recommended by the design based on the number of participants with DLTs observed during this dose evaluation phase ([Table 5.1.2.6-1](#)), then the next lower dose level will be used (360 mg BMS-986207 q3w) for the remaining participants as well as for those currently on treatment. In addition, other lower doses of BMS-986207 (200 mg q3w) than that seen as safe and tolerable may also be tested.

Initially, the first 3 to 4 participants treated in the Triplet Cohort will be evaluated for DLTs. If 0 or 1 DLT is observed during the 6-week DLT period, an additional 3-4 participants will be treated at the same BMS-986207 dose level. If ≤ 1 DLTs are observed out of the first 6 DLT-evaluable participants, the dose will be considered safe. If 2 DLTs are observed out of 6 DLT-evaluable participants, an additional 3-4 participants will be enrolled. If ≤ 3 DLTs are observed out of 9 DLT-evaluable participants, an additional 3 participants will be enrolled. If 2 DLTs are observed out of 12 DLT evaluable participants, the dose level will be considered safe.

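### Table 6 does not describe the Part 1C declare-tolerable rule: at a true DLT rate of 0.30 that rule clears the higher dose in 50.9% of trials, not 77.8%

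*Combined protocol and SAP*

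**What the plan says.** Section 5.1.2.6 introduces the BOIN framework for Part 1C and points to Appendix 12: "The performance of the design based on the operating characteristics is shown in" that appendix. Appendix 12, Section 5 then explains the vocabulary. "Therefore MTD reference below (as in typical multi-dose level design) represents a" tolerable dose, and "a design recommendation to declare a dose as tolerable is based on meeting the same criteria needed to escalate". On the usual BOIN end-of-trial choice of dose it says: "The design MTD selection approach described next, is included for general information on the design; however, it is not used in this study". The simulation settings are that "the maximum sample size is 12. Participants will be enrolled in cohorts of 3".

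Section 5.1 of the same appendix gives Table 6, with true DLT rates, *Selection %* and share treated for two dose levels. It concludes: "The operating characteristics show that the design selects the true MTD (tolerable dose), if any, with high probability".

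The working rule is in Section 5.1.2.6 and Table 5.1.2.6-1. "Initially, the first 3 to 4 participants treated in the Triplet Cohort will be evaluated for DLTs". With at most one event, "DLTs are observed out of the first 6 DLT-evaluable participants, the dose will be considered safe". No declaration is made below 6 evaluable participants. A result of 3/12 or 4/12 is *Stay*, and the text leaves it to discussion. Up to 18 participants may be treated at each dose level.

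**The concern.** Table 6 is offered as the performance of this design, but its outcome measure belongs to a step the appendix says is not taken. Two features show this without any calculation.

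- Selection and early stopping add to 100% in every scenario (60.8 + 31.9 + 7.3; 22.1 + 77.8 + 0.1; 33.7 + 65.2 + 1.1). There is no room for the unresolved result that the rule can produce.
- The 11.8 to 12.0 participants are shared between two doses, whereas the plan allows up to 18 treated at each.

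Declaring a dose tolerable in Part 1C is what allows Part 2C to open. A reader of Table 6 would expect an on-target higher dose to go forward in about 78% of trials, and some dose to go forward in 92.7% to 99.9%. If the stated rule behaves differently, those expectations are wrong.

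**Working it through.** **Step 1. What Table 6 describes.** Inputs from Appendix 12, Section 5: target 0.30, cohorts of 3, 12 participants in total, boundaries 0.236 and 0.359. Three inputs are assumed because the documents do not state them: a start at level 2, re-escalation allowed, and elimination when the posterior probability of a DLT rate above 0.30 exceeds 0.95 under a uniform prior. Exact enumeration with isotonic selection gives the following (level 1 / level 2 / stopped, %):

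| Scenario (true rates) | Recomputed | Table 6 | Share at level 1, recomputed vs Table 6 |
|---|---|---|---|
| 1 (0.30, 0.48) | 60.2 / 32.1 / 7.7 | 60.8 / 31.9 / 7.3 | 40.8 vs 40.8 |
| 2 (0.16, 0.30) | 22.4 / 77.2 / 0.4 | 22.1 / 77.8 / 0.1 | 16.9 vs 16.3 |
| 3 (0.20, 0.35) | 33.7 / 65.1 / 1.2 | 33.7 / 65.2 / 1.1 | 23.3 vs 22.9 |

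Starting at level 1 does not match: by simulation, Scenario 2 becomes 27.9 / 70.8 / 1.3, with 49.2% treated at level 1. So Table 6 has no arithmetic error, but it reports isotonic selection. In Scenario 2, 20.1 of the 77.2 points come from trials that left level 2 and still selected it.

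**Step 2. The stated rule.** Inputs from Table 5.1.2.6-1 at 3, 6, 9 and 12 evaluable: de-escalate at ≥2, ≥3, ≥4, ≥5; declare tolerable at ≤1/6, ≤2/9, ≤2/12. At a true rate of 0.30:

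- P(≤1 of 6) = 0.420. All of these paths pass the look at 3.
- P(2 of 6, with ≤1 in the first 3) = 0.343 × 0.189 + 0.441 × 0.441 = 0.259.
- These go on to 9 and are cleared there if the next 3 have no DLT: 0.259 × 0.343 = 0.089.
- Nothing further is cleared at 12, because anyone reaching 12 already has 3 DLTs.
- P(tolerable) = 0.420 + 0.089 = 0.509. De-escalated 0.401. Unresolved 0.090 (3/12: 0.039; 4/12: 0.050).

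| True DLT rate | Tolerable | De-escalated | Unresolved | Table 6, level 2 |
|---|---|---|---|---|
| 0.16 | 84.3% | 10.8% | 4.8% | – |
| 0.20 | 75.6% | 17.6% | 6.8% | – |
| 0.30 | 50.9% | 40.1% | 9.0% | 77.8% |
| 0.35 | 39.1% | 52.5% | 8.4% | 65.2% |
| 0.48 | 15.8% | 80.1% | 4.2% | 31.9% |

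**Step 3. Sensitivity to the reading, at 0.30.** The first figure clears nothing above 2/12; the second accepts every 3/12 and 4/12.

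| Looks | ≤2/12 only | 3–4/12 accepted |
|---|---|---|
| 3, 6, 9, 12 | 50.9% | 59.9% |
| 3, 6, 9, 12, no declaration at 9 | 45.1% | 59.6% |
| 3, 6, 12 | 45.1% | 61.3% |
| 3, 6, 10, 12 | 48.2% | 58.0% |
| 4, 6, 9, 12 | 48.7% | 55.4% |
| 4, 6, 9, 12, no declaration at 9 | 44.3% | 55.2% |
| 4, 6, 12 | 44.3% | 56.5% |

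The same variants give 33.4–48.9% at 0.35 and 13.2–20.7% at 0.48. Outside the stated looks, omitting the look at 3–4 and accepting all 3–4/12 gives 64.3% (6, 9, 12) or 66.1% (6, 12). Passing over 6 lowers the strict figure, for example to 31.1% with looks at 4, 8 and 12.

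**Step 4. Either dose cleared.** Strictly, this is T(high) + D(high) × T(low), where T is tolerable and D de-escalated, with the same rule at the lower dose and no third level:

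- Scenario 1: 0.158 + 0.801 × 0.509 = 0.565
- Scenario 2: 0.509 + 0.401 × 0.843 = 0.848
- Scenario 3: 0.391 + 0.525 × 0.756 = 0.788

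Accepting all 3–4/12 raises these to 67.9%, 95.7% and 90.7%. Table 6 selects a dose in 92.7%, 99.9% and 98.9%. The gap is 25–36 points in Scenario 1, 4–15 in Scenario 2 and 8–20 in Scenario 3.

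**The case against.** The best defence is disclosure. Appendix 12, Section 5 is headed as a two-dose BOIN simulation, gives its maximum of 12 and cohort size of 3, and says the MTD selection is for general information. On that view Table 6 shows framework characteristics with a caveat, and the fault is loose wording. The caveat, however, never says that Table 6 rests on the unused method, and both Section 5.1.2.6 and Appendix 12, Section 5.1 present the table as this design's performance.

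A second objection is that 50.9% and 77.8% are different quantities, that 3/12 may be accepted after discussion (54.8% on that reading), and that Table 6 has another entry at 0.30: 60.8% for level 1 in Scenario 1. The sequential counterpart of that entry is 0.801 × 0.509 = 40.8%, a gap of 20 points rather than 27. It is fair that the size depends on the entry and the reading, but the direction does not. That the quantities differ is the point itself.

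Third, cohorts of 3–4 can pass over 6, and boundaries beyond 12 are not given. Both are true. Passing over 6 widens the gap. Extrapolating the boundaries to 18 gives roughly 48–53% on the strict count.

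Finally, decisions rest on Table 5.1.2.6-1, and Table 5.1.2.6-2 already gives posterior DLT probabilities. That stands, and it limits the consequence. Posterior probabilities at given results do not say how often a dose is cleared.

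**Conclusion.** The concern holds. Table 6 is correct arithmetic for a procedure the appendix says is not used, and it is cited as the performance of the one that is. For the higher dose it overstates the chance of clearance by 27 points at 0.30, 26 at 0.35 and 16 at 0.48, taking cohorts of 3, a maximum of 12 and 3–4/12 not cleared. No reading tested exceeds 66.1% at 0.30, against 77.8%.

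The identification of Table 6 as isotonic selection from a level 2 start is inferred from reproduction; the conflict between the sections does not depend on it. Unresolved means not settled by the rule, so the 49.1% not cleared at 0.30 is not all de-escalation. The actual rule is more conservative for the higher dose at every rate tabulated, and Table 6 sets no boundary or sample size.

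**What to change.** Replace or supplement Table 6 with the probabilities of declared tolerable, de-escalated and unresolved under the Section 5.1.2.6 rule, for each true DLT rate now shown. State the cohort size, how 3/12 and 4/12 are counted, and whether the maximum is 12 or 18; if 18, add the boundaries beyond 12. Remove or qualify the statement of high probability in Appendix 12, Section 5.1. If Table 6 is kept, label it as the generic two-dose BOIN with isotonic selection and give its starting level.

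Before re-running, reconcile Section 5.1.2.6 with Table 5.1.2.6-1 at 9 evaluable participants: the text enrols 3 more at up to 3/9, while the table declares the dose tolerable at up to 2/9. That difference alone moves the figure at 0.30 from 50.9% to 45.1%.

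The cost is a short exact calculation and one appendix table. The reported clearance of the higher dose falls at 0.30, which looks less favourable, and also at 0.48, which is more reassuring.

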APPENDIX 13 PRELIMINARY SAFETY COHORT

1 PRELIMINARY SAFETY COHORT FOR PHASE 1, PART 1A

1.1 Justification for the Preliminary Safety Cohort (PSC):

The FIH starting dose of BMS-986207 monotherapy, as an immune-mediated anti-cancer agent, was determined using both toxicology- and pharmacology- ([REDACTED] efficacy)-based approaches to ensure participant safety while limiting the number of participants receiving nonpharmacologically active doses. The toxicology-based approach utilized the HNSTD determined from a 1-month repeat-dose toxicity study in cynomolgus monkeys. The pharmacology-based approach leveraged the pharmacology data (ie, [REDACTED] efficacy) obtained from mouse surrogates to project the human effective dose, from which the FIH starting dose was selected. The starting doses determined from both approaches were integrated, and the lower dose of 1 mg/kg (or 80 mg flat dose, assuming an average body weight of 80 kg in cancer participants) was recommended as the starting monotherapy dose for BMS-986207.

Subsequent to discussions with FDA, to further ensure a sufficient safety margin for the monotherapy starting dose, given the absence of previous clinical experience with BMS-986207, a Preliminary Safety Cohort (PSC) was added to the study. In the PSC, a single participant will receive BMS-986207 monotherapy starting at the 2-mg dose, with intra-participant dose escalation to 6 mg, and then to 20 mg. Following a 5-day safety observation period for this participant following the initial administration of the 20-mg dose, 2 additional participants will begin the study at the 20-mg BMS-986207 dose level.

At the conclusion of the 4-week DLT period for these 3 participants in the PSC, which respectively begins with the first administration of the 20-mg dose for each of the 3 participants in the PSC, if no DLT is observed, the main study protocol will begin with participants receiving BMS-986207 monotherapy at the 80 mg dose level. If a DLT is observed in the PSC, the BLRM will be initiated. A decision whether to treat additional patients at the same dose level, or escalate the dose, will be based on a recommendation from the BLRM and overall clinical assessment with all the safety, pharmacokinetic [REDACTED] data..

1.2 Study Design for PSC:

In the PSC, the first cohort of 3 participants will be administered intravenous (IV) doses of BMS-986207 as follows:

The starting dose of 2 mg of BMS-986207 will be assigned to the first participant, followed by intra-participant dose escalation after 2 weeks to 6 mg, and then 2 weeks later to 20 mg, if no DLTs are observed in any of the dose intervals. After the participant clears a 5-day safety observation period at the 20-mg dose level, 2 additional participants will be enrolled at the 20-mg dose level. The 4-week DLT period for all participants in the PSC begins with the first 20-mg dose administration. For these PSC participants, subsequently, flat dose levels of 20 mg will be given q2w, in 8-week cycles, for up to 3 cycles of study therapy.

All the procedures for this PSC, in regard to the study design, study population, treatment, discontinuation criteria and study assessments/procedures, are the same as described in respective

Sections 5, 6, 7, 8 and 9 of the main protocol. The objectives, endpoints, and statistical considerations (Section 4 and Section 10) of the main protocol also apply to the PSC. The only exceptions to the provisions of the main protocol for the PSC are the Treatment Periods and the Pharmacokinetics, Immunogenicity [REDACTED] sampling schedules for the first participant undergoing intra-participant dose escalation. These exceptions to the main protocol are detailed below.

1.2.1 Treatment Periods

The first participant will receive BMS-986207 as monotherapy at the starting dose of 2 mg. The infusion will take place over 5 minutes and will require a 60-minute observation period following the completion of the infusion. A 60-minute post infusion safety observation period is considered appropriate given BMS-986207 is a fully human monoclonal antibody that is an antagonist (not an agonist) and has a low likelihood of resulting in infusion reactions. The participant will follow the assessments and procedures described below and, after 2 weeks, if no DLT occurs in that 2-week interval, the participant will proceed to the next dose infusion of BMS-986207 at 6 mg. This infusion will take place over 10 minutes and will require a 60-minute observation period following the completion of the infusion. After another 2-week observation period, if no DLT occurs in that 2-week interval, the participant will then escalate to the next dose level of 20 mg. At this dose level, a treatment cycle will be comprised of 4 doses of BMS-986207 administered q2w. At the 20-mg dose level, BMS-986207 infusions will take place over 60 minutes and will require a 60-minute observation period following the completion of the infusion for the first 4 doses of Cycle 1 for the participant, as described in Section 5.1.2 of the main protocol. After the first participant clears a sentinel period of 5 days with no safety issues observed, 2 new participants will be enrolled in the study to start treatment of BMS-986207 at the 20-mg dose level. These 2 participants will follow all the same study procedures and evaluations as described in the main protocol. The PSC Treatment Scheme is summarized in Table 1.2.1-1 below.

Vital signs and pulse oximetry monitoring, as outlined in Section 2, will be performed for all dose level administrations of BMS 986207.

Table 1.2.1-1: Preliminary Safety Cohort Treatment Scheme

Patient	Treatment Time	Dose (mg)	Infusion Time, min
[REDACTED]	Day 1	2	5
	Day 15	6	10
	Day 29	20	60
	> Day 34 ^b	20	60
	> Day 34 ^b	20	60

^b Patient [REDACTED] could be enrolled at 20 mg dose level after Patient [REDACTED] has cleared a 5 day sentinel period after he received the first dose of 20 mg. These two participants will follow all the same study procedures and evaluations as described in the main protocol.

1.2.2 Study assessments and procedures:

The first participant enrolled in the PSC will follow the same study assessments and procedures for respective day number of the cycle as described in [Section 9](#) and as outlined in [Section 2](#) of the main protocol, including physical exams and safety laboratory assessment, with the exception of pharmacokinetic and immunogenicity sample collections, as detailed below in Table 1.2.2-1, and triplet ECGs which will be performed on both CAD1 and CBD1.

Table 1.2.2-1: Pharmacokinetic and Immunogenicity Sampling Schedule for PSC - Intra-Participant Dose Escalation

Study Cycle (C) and Day (D) of Sample Collection	Days on Treatment	Event	Time (relative to dose administration) Hour: Min	BMS-986207 Blood Sample (all participants)	BMS-986207 ADA Samples (all participants)
CAD1 (2 mg)	1	Predose ^a	00.00	X	X
		EOI ^b	60 to 90 min	X	
			4:00	X	
CAD8 ^c (2 mg)	8		168:00	X	
CBD1 (6 mg)	15	Predose ^a	00: 00	X	X
		EOI	01:00	X	
			4:00	X	
CBD8c (6 mg)	22		168:00	X	
C1D1 (20 mg)	29	Predose ^a	00: 00	X	X
		EOI ^b	01:00	X	
			4:00		
C1D8	36		168: 00	X	
C2D1	85	Predose ^a	00: 00	X	
		EOI ^b	60 to 90 min	X	
C3D1	141	Predose ^a	00: 00	X	X
C4D1		Predose ^a	00: 00	X	X
C5D1		Predose ^a	00: 00	X	X
EOT				X	X
30-day follow-up				X	X
60-day follow-up				X	X

Abbreviations: ADA, anti-drug antibody, BMS, Bristol-Myers Squibb; C, cycle; D, day; EOI, end of infusion, EOT, end of treatment; PSC, preliminary safety cohort.

- ^a Predose: All predose samples for BMS-986207 should be taken prior to the start of the infusion. If the predose sample has been taken, however, and an unscheduled, missing, or delayed dose occurs, an additional predose sample shall be taken.
- ^b EOI samples for BMS-986207 should be collected immediately prior to stopping the infusion (preferably within 2 minutes prior to the end of the infusion). If the end of infusion is delayed to beyond the nominal infusion duration, the collection of this sample should also be delayed accordingly.
- ^c Day 8 sample may be taken during Days 7-9 of a cycle.

